### 2.2.1. Overview of Current Therapeutic Interventions and Rationale for Use of Volixibat in ICP

Treatment of ICP is directed toward 2 main goals: reducing symptoms in the expectant mother, in particular cholestatic pruritus, and reducing adverse perinatal outcomes.

Off-label use of ursodeoxycholic acid (UDCA; except in France where it is approved for the treatment of ICP) has been the only option consistently proposed in guidelines as a treatment option for ICP. However, evidence is mixed regarding its benefit. Two Cochrane systematic reviews of the effectiveness of UDCA for ICP have concluded that it might ameliorate pruritus to a small extent but that definitive evidence for improvement in perinatal outcomes was absent (Gurung et al. 2013; Walker et al. 2020). Additionally, a recent meta-analysis of 13 studies also concluded that UDCA did not significantly improve maternal or fetal outcomes (Shen et al. 2019). In a recent double-blind, multicenter, randomized placebo-controlled study that enrolled 605 women with ICP in the United Kingdom (Chappell et al. 2019), UDCA was not effective in reducing a composite of adverse perinatal outcomes, defined as in utero fetal death or neonatal death, preterm delivery, or neonatal unit admission. Although UDCA appeared to be safe, it had no clinically meaningful effect on maternal itch symptoms. It did not reduce maternal sBA concentrations, and the reduction in ALT was of uncertain clinical significance. In contrast to the randomized, placebo-controlled data from PITCHES, a recent individual patient data meta-analysis suggested that UDCA treatment in patients with ICP was associated with a statistically significant reduction in spontaneous preterm births in singleton pregnancies with initial sBA levels  $\geq 40$   $\mu\text{mol/L}$  without a significant reduction in stillbirth, compared with no UDCA treatment (Ovadia et al. 2021). Notably, the patients not treated with UDCA were treated with placebo, S-adenosyl-methionine, and/or other off-label therapies for ICP.

In another small survey-based study, rifampicin use in combination with UDCA was associated with lower sBA levels in women with ICP (Geenes et al. 2015). However, rifampicin treatment can be associated with hepatotoxicity, which affected up to 13% of participants in a study of PBC (Bachs et al. 1992), and the potential fetal side effects are unknown.

Besides UDCA and rifampicin, cholestyramine, dexamethasone, and S-adenosyl-L-methionine have demonstrated some evidence of maternal benefit in ICP. However, none of the aforementioned therapeutic options is considered as first-line treatment (EASL 2009; Tran et al. 2016; Bicocca et al. 2018). Vitamin K supplementation is also frequently used in cases of vitamin K deficiency to limit the risk of intrapartum and postpartum hemorrhage.

Temporary relief from pruritus may be achieved in some women through the use of over-the-counter topical treatments or antihistamines. However, such therapeutic options provide limited and inconsistent relief and do not address the underlying pathologic mechanism of pruritus and the resulting potentially serious or fatal consequences for the fetus.

In summary, UDCA use has shown limited and conflicting supporting evidence. As a result, patients with ICP often cycle through UDCA and off-label therapies without relief, which may result in a decision to induce delivery preterm, increasing the risk of preterm-associated morbidity and mortality to the fetus (Chappell et al. 2019).

Although recommendations are inconsistent across guidelines and the practice is not evidence based, active management of pregnancy by early elective delivery between 36 and 38 weeks is performed on a case-by-case basis in some regions of the world and seems to have been

successful at reducing the intrauterine death rate (EASL 2009; Tran et al. 2016; Bicocca et al. 2018; ACOG 2019). For example, a recent guidance from the Society for Maternal-Fetal Medicine (Lee et al. 2021) recommends elective delivery for patients with ICP and total sBA levels of <100 µmol/L between 36 weeks 0 days and 39 weeks 0 days of gestation; patients with total sBA levels ≥100 µmol/L should be offered delivery at 36 weeks of gestation. This practice is associated with its own risks for the baby, ranging from short-term neonatal problems to long-term issues such as cerebral palsy; disorders of psychological development, behavior, and emotion; and other major disabilities such as impaired vision and hearing (Moster et al. 2008; Saigal and Doyle 2008; MacKay et al. 2010; Quigley et al. 2012).

In summary, although symptoms are transient for the mother, ICP is associated with increased maternal morbidity, increased risk of life-threatening or even fatal sequelae for the fetus, and chronically debilitating consequences for surviving infants. This is reflected in the widespread policies to manage severe cases of ICP by elective early delivery between 36- and 38-weeks' gestational age or earlier to reduce the risk of late stillbirth and alleviate maternal symptoms. This practice is not evidence based (EASL 2009; Tran et al. 2016; Bicocca et al. 2018; ACOG 2019) and is associated with potentially severe and/or chronic sequela.

The current study is designed to assess the potential of volixibat to reduce maternal pruritus and fetal morbidity and mortality associated with ICP, which would provide a significant efficacy benefit over currently utilized therapies. In ICP, lowering of (or mitigating potential further increases in) maternal sBA would be expected to ameliorate the increased risk of adverse perinatal outcomes associated with increased sBA levels by promoting restoration of the physiologic transplacental gradient and alleviating the accumulation of toxic bile acids in the fetus. Given the evidence supporting the role of elevated sBA as a driver of adverse perinatal outcomes, the mean change in total maternal sBA concentration has been selected as the primary endpoint as a surrogate for clinically relevant perinatal outcomes. Perinatal outcomes will also be directly assessed using a composite measure as a key secondary efficacy endpoint.

The current study design is divided into 2 parts. Part 1 is an open-label phase that provides real-time assessments of safety/tolerability of volixibat 20 mg and 80 mg as well as data for dose exploration and selection for Part 2 of the study. Part 2 is a randomized, double-blind, placebo-controlled phase for confirmatory analysis comparing the selected volixibat dose with placebo for superior efficacy.

### 2.3. Volixibat Pharmaceutical and Therapeutic Background

Volixibat is an inhibitor of the ileal bile acid transporter (IBAT). Inhibition of IBAT interrupts normal enterohepatic recirculation of bile acids, significantly increasing the amount of bile acid excreted in feces in treated participants and lowering circulating bile acid levels. Bile acids and their recirculation are understood to be at the center of cholestatic pruritus pathophysiology, and IBAT inhibitors similar to volixibat, such as maralixibat and GSK2330672, have demonstrated efficacy in pruritus and sBA reductions associated with progressive familial intrahepatic cholestasis (PFIC), Alagille syndrome, PBC, and PSC (Hegade et al. 2017; Thompson et al. 2019; Bowlus et al. 2019; Gonzales et al. 2019a, 2019b; Mayo et al. 2019). In nonclinical and clinical studies, treatment with volixibat has been shown to affect key pharmacodynamic (PD) parameters associated with IBAT inhibition, similar to other IBAT inhibitors. These include increased fecal bile acid (fBA) excretion, in conjunction with increases

in 7 $\alpha$ -hydroxy-cholesten-3-one (7 $\alpha$ C4) and decreases in low-density lipoprotein (LDL) cholesterol; both are PD measures indicating increased bile acid synthesis to compensate for increased bile acid excretion and a reduction in the bile acid pool in the body caused by effective IBAT inhibition.

UDCA is used as a potential treatment for ICP despite evidence of limited efficacy (see [Section 2.2.1](#)). The exact mechanism by which UDCA could provide benefit in ICP and other cholestatic diseases is not understood but could be due to its relatively hydrophilic nature compared with other bile acids. While volixibat inhibits the recirculation of bile acids, it is important to note that no drug-drug pharmacokinetic (PK) interaction is expected between volixibat and UDCA. The preferred substrates for IBAT are conjugated bile acids. Since UDCA is a non-conjugated bile acid likely absorbed through passive diffusion, IBAT inhibition is not predicted to have an effect on the bioavailability of oral UDCA. Published modeling of the pharmacokinetics of UDCA and its metabolites in the presence and absence of IBAT inhibition predicts the absence of a PK interaction ([Zuo et al. 2016](#)). In addition, clinical UDCA PK data in the context of an IBAT inhibitor dosed in patients with PBC showed no drug-drug interaction between UDCA and the IBAT inhibitor ([Hegade et al. 2017](#)).

A detailed description of the chemistry, pharmacology, efficacy, and safety of volixibat is provided in the Investigator Brochure (IB).

## **2.4. Key Nonclinical and Clinical Studies**

This is the first study evaluating volixibat for the treatment of participants with ICP. An extensive nonclinical PK; absorption, distribution, metabolism, and excretion (ADME); and safety package has been completed on volixibat, including a full battery of safety pharmacology studies, 4 different types of genotoxicity tests, and chronic general toxicity testing in rats (up to 26-week duration) and in dogs (up to 39-week duration). To prepare for the proposed ICP clinical study in the more vulnerable population of pregnant women, the battery of developmental and reproductive toxicology (DART) testing was also expanded, including fertility and early embryonic development testing in rats, embryo/fetal development testing in rats and rabbits, and prenatal and postnatal development testing (including maternal function) in rats. No concerning toxicities were observed in any of these studies, and very large safety margins (14-160X depending on animal study, under the assumption of a human dose of 80 mg twice daily [BID]) were established between the animal doses and the highest proposed human dose.

Volixibat is minimally absorbed after oral dosing at all doses tested. The highest plasma concentration that has been recorded in previous clinical studies is 0.64 ng/mL (0.79 nM). Food does not affect the absorption of volixibat. Elimination is via fecal excretion with negligible metabolism and urinary excretion (70% eliminated in the feces within 24 hours, >90% from feces over the full course of a clinical mass balance study). Metabolism and urinary excretion are negligible.

Volixibat administration reduces systemic bile acids in all populations and species studied as evidenced by rapid and significant fecal excretion and consistent changes in markers indicative of an interruption of enterohepatic recirculation bile acids across healthy volunteers and participants with nonalcoholic steatohepatitis (NASH). In addition, in instances where

participants demonstrated elevated baseline levels of sBA, rapid and significant decreases in sBA were observed on volixibat treatment, consistent with the significant decreases in sBA observed in a nonclinical model of mild cholestasis. The consistent PD effects of volixibat observed on bile acids and serum  $7\alpha C4$  in previous clinical studies indicate that volixibat inhibits bile acid reabsorption and supports the potential utility in treating patients with ICP.

Refer to the Volixibat IB for detailed information regarding nonclinical and clinical studies with volixibat.

## 2.5. Benefit/Risk Assessment

By virtue of volixibat's ability to inhibit IBAT-mediated bile acid reabsorption, there is an increase in bile acid excretion via the intestine and feces that results in lower bile acid levels in the serum. It is hypothesized that these net reductions in bile acid levels will, in turn, have a beneficial impact on pathological processes and symptoms in patients with diseases associated with elevated bile acid levels, such as ICP. Volixibat has been well tolerated in clinical studies to date with the most common adverse events (AEs) being mild and transient gastrointestinal (GI) symptoms. No clinically significant safety concerns were observed based on review of safety data across all participants exposed to volixibat.

As stated above, clinical data suggest extremely low systemic exposure to volixibat, because it is minimally absorbed with concentrations obtained in humans at the intended clinical doses being typically below the lower limit of quantitation (LLOQ; LLOQ=0.05 ng/mL). Taken together with the findings from the battery of DART testing, there is minimal risk of exposure to the fetus or harm to the fetus upon potential exposure to volixibat.

Based upon the above, the benefit-risk profile of volixibat in patients with ICP, as well as in their neonates, is predicted to be favorable. More detailed information about the known and expected benefits and risks, including the expected adverse reactions of volixibat, may be found in the Volixibat IB.

## 3. OBJECTIVES AND ENDPOINTS

The following objectives and endpoints will be evaluated in participants who meet study eligibility criteria.

### 3.1. Primary Objective and Endpoint

Part 1:

- To assess the safety and tolerability of volixibat in participants with ICP on the basis of the following endpoints:
  - Proportion of participants experiencing one or more of the following:
    - Treatment-emergent adverse events (TEAEs), serious adverse events (SAEs), adverse events of special interest (AESIs), events of clinical interest (ECIs), and AEs that lead to discontinuation of study drug
    - Clinically significant laboratory abnormalities

Part 2:

- To assess the efficacy of volixibat on the reduction of elevated sBA concentrations in participants with ICP on the basis of the following endpoint:
  - Mean change from baseline to Week 3 of the treatment period in total sBA concentration

### 3.2. Secondary Objectives and Endpoints

The following secondary objectives and endpoints are applicable in Part 1 and Part 2.

- To assess the efficacy of volixibat on pruritus due to ICP on the basis of the following endpoint:
  - Mean change from baseline to Week 3 of the treatment period in the weekly average worst daily itch score as measured by the Adult Itch Reported Outcome (ItchRO)
- To assess the impact of volixibat on a composite perinatal outcome in participants with ICP on the basis of the following endpoints:
  - Proportion of participants experiencing one or more of the following:
    - Perinatal death, defined as in utero fetal death after randomization or known neonatal death up to 28 days after birth
    - Spontaneous preterm delivery, defined as delivery at <37 weeks' gestational age following spontaneous onset of preterm labor or preterm premature rupture of the membranes (PPROM)
    - Iatrogenic preterm delivery attributable to ICP or ICP-related complications, defined as delivery at <37 weeks' gestational age resulting from medical intervention (i.e., augmentation/induction of labor or cesarean delivery without prior spontaneous onset of preterm labor or PPROM with one or more of the following as the indication for delivery):
      - Diagnosis of ICP with or without suspected fetal compromise
      - Persistently elevated/increasing sBA
      - Worsening hepatic function
      - Intolerable maternal ICP symptoms
    - Neonatal unit admission for  $\geq 12$  hours from birth until hospital discharge for one or more of the following indications:
      - Respiratory insufficiency/failure with requirement for oxygen supplementation
      - Noninvasive or invasive respiratory support
      - Hemodynamic instability or shock requiring clinical intervention
      - Metabolic acidosis or signs of asphyxia

- Proven infection
- Hypoglycemia or feeding problems requiring intravenous (IV) fluids or tube feeding
- Meconium-stained amniotic fluid and/or its sequelae (e.g., meconium aspiration, etc.)

### 3.3. Safety Objective and Endpoints

- To assess the safety and tolerability of volixibat in participants with ICP on the basis of the following endpoints in Part 2:
  - Incidence of TEAEs, SAEs, AESIs, ECIs, and AEs that lead to discontinuation of study drug
  - Incidence of clinically significant laboratory abnormalities

### 3.4. Exploratory Objectives and Endpoints

The following exploratory objectives and endpoints are applicable to Part 1 and Part 2:

- To assess volixibat drug levels in maternal and fetal plasma and PD markers in maternal blood in participants with ICP on the basis of the following endpoints:
  - Volixibat concentrations in maternal and fetal plasma (from umbilical cord sampling)  
Note: Assessment of maternal/fetal volixibat drug levels is a secondary objective for Part 1.
  - Change in biomarkers of bile acid synthesis, inflammation, and pruritogens
  - Proportion of participants with sBA <40 µmol/L at end of the treatment period
- To assess the longer-term efficacy of volixibat in participants with ICP on the basis of the following endpoints:
  - Mean change from Week 3 to end of treatment period in total sBA concentration
  - Mean change from baseline to end of treatment period in total sBA concentration
  - Association between changes from baseline to Week 3 in total sBA and ItchRO as well as their association with the composite perinatal outcome
- To assess the effect of volixibat on additional perinatal outcomes on the basis of the following endpoints:
  - Mean gestational age at delivery
  - Proportion of participants with an early term delivery (37–38 weeks 6 days, inclusive)
  - Proportion of participants with a full-term delivery (≥39 weeks)
  - Proportion of participants experiencing a perinatal death
  - Proportion of participants with a spontaneous preterm delivery

- Proportion of participants with an iatrogenic preterm delivery attributable to ICP
- Proportion of neonates requiring neonatal intensive care unit (NICU) admission for  $\geq 12$  hours between birth and hospital discharge
- Proportion of neonates with meconium-stained amniotic fluid at delivery
- Proportion of participants requiring rescue medication for ICP
- Proportion of neonates with Apgar score  $< 7$  at 5 minutes of life
- Mean birth weight percentile
- Mean placental weight percentile
- Proportion of neonates with umbilical cord pH  $< 7.0$  at birth
- Means for umbilical cord blood sBA, total cholesterol, LDL cholesterol, and glucose
- Mean maternal estimated blood loss at delivery
- Mean time from randomization to delivery
- To evaluate the effect of volixibat on additional measures of pruritus efficacy and quality of life in participants with ICP on the basis of the following endpoints:
  - Change from baseline in the 5-D Itch Scale
  - Change from baseline in Clinician Scratch Scale (CSS)
  - Change from baseline in EuroQoL 5-dimension, 5-level (EQ-5D-5L)
  - Change from baseline in Patient-Reported Outcomes Measurement Information System (PROMIS®) Short Form (SF) Fatigue 7a
  - Change from baseline in PROMIS SF Sleep Disturbance
  - Change from baseline in Patient Impression of Severity-Itch (PIS-Itch)
  - Patient Global Impression of Change-Itch (PGIC-Itch)
- To assess the impact of volixibat on healthcare utilization in participants with ICP on the basis of the following endpoints:
  - Number and duration of medical care encounters, including surgeries and other selected procedures (inpatient and outpatient)
  - Dates and duration of hospitalization (total days or length of stay, including duration by wards [e.g., intensive care unit])
  - Number and type of diagnostic and therapeutic tests and procedures
  - Outpatient medical encounters and treatments (including physician or emergency department visits, tests and procedures, and medications)

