Although ICP resolves rapidly following delivery, it is associated with an increased risk of future morbidity, including higher incidence of hepatobiliary diseases such as hepatitis, fibrosis, and gallstones and increased risk of liver and biliary tree cancer, immune-mediated disease, and cardiovascular disease. Moreover, oral contraceptives, in particular those containing estrogens, may cause recurrence of symptoms, and guidelines recommend the use of alternative methods of contraception ([Bicocca et al. 2018](#)). Furthermore, patients with ICP can suffer from jaundice or present with vitamin K deficiency, which can lead to prolonged coagulation time and increase the risk of intrapartum and postpartum hemorrhage ([Mohan et al. 2019](#)).

Generally speaking, ICP is diagnosed if sBA levels are approximately  $\geq 10$   $\mu\text{mol/L}$  in a pregnant woman with new onset of pruritus during pregnancy and no other known pathology thought to be responsible for the laboratory findings and/or symptoms ([Bicocca et al. 2018](#)). ICP can be classified as mild or severe depending on the level of accumulation of sBA, with 40  $\mu\text{mol/L}$  often used as the threshold value that is considered severe ([Bicocca et al. 2018](#)).

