#### Type of Participant and Disease Characteristics

3. Diagnosis of ICP, as characterized by the following:  
Onset of pruritus during pregnancy with no known etiology other than ICP (e.g., pruritic urticarial papules and plaques of pregnancy, pruritic folliculitis, uncontrolled thyroid disease, etc.)  
sBA level  $\geq 10$   $\mu\text{mol/L}$  at any point during the current pregnancy  
Absence of known pathology that may produce similar laboratory findings/symptoms; these include but are not limited to other cholestatic disorders such as PBC and PSC  
Note: Suspicion of transient hypercholanemia should be discussed with medical monitor to confirm participants eligibility.

4. Part 1:
  - sBA of  $\geq 10$   $\mu\text{mol/L}$  as assessed by the central laboratory during the screening period or local laboratory at any time during the current pregnancy
- Part 2:
  - sBA level  $\geq 20$   $\mu\text{mol/L}$  as assessed by the central laboratory during the screening period
  - Documentation of historic or local sBA level is required to confirm participant eligibility before randomization.
  - Laboratory assessments may be repeated at the investigator's discretion before randomization.
  - Participants already on UDCA at the time of the screening visit shall be eligible for Part 1.
5. Willing and able to refrain from the use of any of the following for the duration of the study: statins, rifampin, bile acid sequestrants (e.g., cholestyramine), peroxisome proliferator-activated receptor (PPAR) agonists/fibrate drugs (e.g., fenofibrate, bezafibrate), S-adenosyl methionine
  - Participants requiring local/systemic corticosteroids or selective serotonin reuptake inhibitors (e.g., sertraline) for the management of non-cholestatic, non-pruritic conditions must have been on a stable dose for at least 1 week before screening and be willing to remain on a stable dose for the duration of the study to be considered eligible.
  - Administration of isolated doses of corticosteroids for obstetric indications (e.g., promotion of fetal lung maturity for anticipated preterm delivery) is permitted
6. Part 2 only: Willing and able to enter daily patient-reported outcome (PRO) information in an eDiary for the duration of the study and completes  $\geq 70\%$  of the eDiary ItchRO assessments during the screening period. A minimum of 4 once-daily ItchRO entries are required during screening.

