## 10.1. Sample Size Determination

Part 1 of the study is designed for estimation without formal statistical testing; hence, there are no formal power considerations. For example, with 20 participants per group and assuming a standard deviation of 25 for each group, a 95% CI for the mean for each volixibat arm would have a half width of 11.

For the power calculations for Part 2, it is assumed that only a single dose will be selected at the end of Part 1, and a 2-sided alpha 0.05 will be used to test whether there is a difference between the 2 groups. Thus, for Part 2, a sample size of 100 participants per arm has 80% power to detect mean difference of 10 with standard deviation of 25. Power was calculated using SAS, version 9.4.

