#### 10.4.1.4. Exploratory Efficacy Endpoints

The exploratory efficacy endpoints are defined in [Section 3.4](#). The change in total sBA from Week 3 (primary endpoint) to delivery will be considered, and the difference between treatment groups will be tested using a randomization-based version of rank analysis of covariance (ANCOVA; [Stokes et al. 2012](#)). In a similar manner, the change from baseline in total sBA concentration to the time of delivery will also be explored. An additional analysis will be performed that examines the change from baseline to delivery but that averages across the last 2 time points on or prior to delivery. Similar analyses will be performed for Adult ItchRO. Associations between the changes from baseline to Week 3 in total sBA and Adult ItchRO will be assessed using either Pearson’s or Spearman’s correlation coefficient. “Responder” analyses for composite perinatal outcomes will be performed using baseline sBA and ItchRO and the change at Week 3 values in sBA and ItchRO as covariates and, separately, using the Week 3 values themselves (instead of the change at Week 3).

Change in biomarkers of bile acid synthesis, inflammation, and pruritogens as well as the proportion of participants with sBA <40 µmol/L at the end of the treatment period will also be explored. The change in biomarkers will follow the same approach as other exploratory efficacy endpoints described above. The proportion of participants with sBA <40 µmol/L at the end of the treatment period will be analyzed in the same manner as the secondary efficacy endpoint for composite perinatal outcomes.

Further exploratory efficacy endpoints include continuous and binary endpoints on additional perinatal outcomes. The analysis of continuous endpoints will follow the same approach as other exploratory efficacy endpoints described above. Binary outcomes will be analyzed in the same manner as the secondary efficacy endpoint for composite perinatal outcomes. Additional details will be included within the SAP.

The secondary endpoint of composite perinatal outcomes will also be explored using an ordinal scale, with ranks assigned according to the severity of the outcomes specified within [Section 3.2](#).

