### 3.3. Strata and Covariates

Participants will be randomly assigned to treatment groups via the interactive voice or web response system (IXRS).

- For the primary cohort, a dynamic allocation method, introduced by Pocock and Simon (1975) will be adopted to balance participant assignment between treatment arms based on the following factors: gestational age (<32 weeks or ≥32 weeks) at randomization, presence/absence of gestational diabetes, and highest sBA before randomization (<40 µmol/L, ≥40 µmol/L to <100 µmol/L, or ≥100 µmol/L) after confirmation of study eligibility. Participants with highest pre-randomization sBA <40 µmol/L shall comprise no more than 33% of the primary cohort for Part 1 and Part 2, respectively.
  - For Part 1, in a 1:1:1 ratio via a computer-generated randomization schedule to receive volixibat 20 mg BID, volixibat 80 mg BID, or placebo BID
  - For Part 2, in a 1:1 ratio via a computer-generated randomization schedule to receive the selected volixibat dose (determined at the interim analysis) or placebo BID
- For the supplemental cohort, participants will be randomized with stratification (based on gestational age at randomization and presence/absence of gestational diabetes) after confirmation of study eligibility in a 1:1 ratio via a computer-generated randomization schedule to receive volixibat 20 mg BID or 80 mg BID.

Efficacy endpoints will be evaluated using stratification factors as covariates or stratification variables for analyses, as specified in [Section 6](#). If there is an imbalance in presumed prognostic baseline characteristics between treatment groups, efficacy evaluations may be performed that include these baseline values in efficacy analysis models as covariates; these evaluations will be considered sensitivity analyses.

For efficacy endpoints, the baseline value of the efficacy variable(s) will be included as a covariate in the efficacy analysis model.

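### The exploratory endpoint of sBA <40 µmol/L at end of treatment merges reaching that level with never having been above it, and the SAP leaves unclear whether its test is stratified by sBA

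*Protocol*

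**What the plan says.** **Endpoint.** Protocol 3.4 defines the "Proportion of participants with sBA <40" µmol/L at the end of the treatment period. SAP 1.1.4 and 6.3 repeat it. None of these sets a condition on baseline sBA. The list opens: "The following exploratory objectives and endpoints are applicable to Part 1 and Part 2".

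**Who can start below 40.** Part 2 requires sBA ≥20 µmol/L "as assessed by the central laboratory during the screening period" (Protocol 5.1, criterion 4). Part 1 requires ≥10 µmol/L, which may be a local value from any time in the pregnancy. Protocol 6.3.1 balances Part 2 allocation on highest sBA before randomization (<40, 40 to <100, ≥100), so a group below 40 is expected. Part 1 allocation does not use sBA. SAP 3.3 says that participants whose highest value is <40 "shall comprise no more than 33% of the primary cohort for Part 1 and Part 2, respectively". That SAP is based on protocol Version 1, and the current protocol has no such cap.

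**Why 40.** Protocol 2.1 describes 40 µmol/L as "often used as the threshold value that is considered severe".

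**Analysis.** Protocol 10.4.1.4 states that this proportion "at the end of the treatment period will be analyzed in the same manner as the secondary efficacy endpoint for composite perinatal outcomes", which means a stratified CMH test. The protocol does not name the strata. SAP 6.2, when defining the Mantel-Haenszel difference, names gestational age, baseline ItchRO and gestational diabetes, and indexes the strata from 1 to 12. The van Elteren sample code in SAP Appendix 3 uses the same three factors. SAP 3.3 says that efficacy endpoints will use the stratification factors as covariates or strata.

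**The concern.** A participant who starts at 20 µmol/L and ends at 39 counts as a success, as does one who falls from 120 to 39. The first was never above the threshold and has worsened; the second has crossed it. Because 40 is the protocol's marker of severe disease, a reader will take the proportion as showing how often volixibat brings severe disease under control. As defined, it cannot show that, since it also counts participants who were never above 40 at baseline.

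The absolute percentages depend on how many mild cases were enrolled. In Part 1, where allocation ignores sBA, the 20 mg and 80 mg proportions can differ through baseline mix alone, in data that inform dose selection.

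Baseline sBA is also likely to be the strongest predictor of this outcome. If the CMH strata omit it, the test gives up precision that the allocation scheme was set up to provide.

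**Working it through.** **The plan's own power figure.** It concerns the primary endpoint, mean change in sBA: "a sample size of 100 participants per arm has 80% power to detect mean difference of 10 with standard deviation of 25". The standard error is 25 × √(2/100) = 3.536, and 10/3.536 − 1.960 = 0.868, giving power 0.807. The required size is 2 × (25 × 2.802/10)² = 98.1, so 99 per arm. The figure reproduces. The plan states no power for the <40 endpoint.

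**The count of strata.** The allocation factors are gestational age (2 levels), gestational diabetes (2) and highest sBA (3): 2 × 2 × 3 = 12. The factors listed in SAP 6.2, with ItchRO at the two levels of SAP 3.4, give 2 × 2 × 2 = 8. The index of 12 fits the allocation factors and not the printed list.

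**Dependence on baseline mix.** The documents give no success rates, so all rates below are assumptions. Let f be the share starting <40. Assume 95% of them end <40 in both arms, and that 50% (volixibat) versus 25% (placebo) of those starting ≥40 end <40. Then:

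- each arm's proportion is f × 0.95 + (1 − f) × its success rate among those starting ≥40;
- the difference is (1 − f) × 25 points.

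Power uses the two-proportion formula, Φ[(d − 1.96·se₀)/se₁], where se₀ is the pooled null standard error and se₁ the unpooled one, with two-sided alpha 0.05 and 100 per arm.

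| f | Placebo | Volixibat | Difference (points) | Power, all, unstratified | Power, baseline ≥40 only |
|---|---|---|---|---|---|
| 20% | 39.0% | 59.0% | 20.0 | 0.81 | 0.91 |
| 33% | 48.1% | 64.9% | 16.8 | 0.67 | 0.86 |
| 50% | 60.0% | 72.5% | 12.5 | 0.46 | 0.74 |

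For f = 33%, all participants:

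- se₀ = √(0.565 × 0.435 × 2/100) = 0.0701
- se₁ = √((0.481 × 0.519 + 0.6485 × 0.3515)/100) = 0.0691
- (0.1675 − 1.96 × 0.0701)/0.0691 = 0.435, power 0.67

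For f = 33%, restricted to 67 per arm:

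- se₀ = √(0.375 × 0.625 × 2/67) = 0.0836
- se₁ = √((0.1875 + 0.25)/67) = 0.0808
- (0.25 − 1.96 × 0.0836)/0.0808 = 1.065, power 0.86

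**Stratifying by sBA.** Simulating the CMH test with baseline <40 and ≥40 as strata, same rates, gives about 0.82 at f = 33% and 0.66 at f = 50%. The formula lets the mix vary by chance. With the mix fixed at 33 per arm, closer to what balanced allocation delivers, the unstratified test simulates at about 0.72. The gain from stratifying at f = 33% is thus 10 to 15 points (0.82 − 0.72 to 0.82 − 0.67).

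**If volixibat also prevents rises.** Keep 50% versus 25% above 40 and 95% maintenance on volixibat, and lower maintenance on placebo:

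| f | Maintenance, volixibat vs placebo | All, unstratified | Baseline ≥40 only |
|---|---|---|---|
| 33% | 95% vs 85% | 0.82 | 0.86 |
| 33% | 95% vs 80% | 0.87 | 0.86 |
| 33% | 95% vs 75% | 0.92 | 0.86 |
| 50% | 95% vs 80% | 0.84 | 0.74 |
| 50% | 95% vs 75% | 0.91 | 0.74 |

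A second set of rates (20% versus 40% above 40, f = 33%) shows the same pattern. With 100% maintenance in both arms, power is 0.47 unstratified, 0.72 stratified and 0.72 restricted. With maintenance of 70% on placebo versus 90% on volixibat, it is 0.81, 0.90 and 0.72.

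**The case against.** The strongest reply is that staying below 40 is itself an outcome worth counting. Protocol 2.2.1 treats limiting further rises in maternal sBA as an expected benefit, and a participant starting below 40 must still be there at end of treatment to count. Restricting to baseline ≥40 would discard that information and, as shown, can lose power. This stands, and it is why the all-participant analysis should be kept.

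A second reply is that the plan does not ignore baseline sBA. The supportive logistic model in SAP 6.2 includes it, SAP 3.4 explores subgroups by the randomization factors, and SAP 3.3 with the index of 12 points to sBA strata. This also stands. A reader might infer that nothing in the plan separates the two groups, but these sections say otherwise. What remains is that the printed list of strata contradicts the count, and no planned display is labelled as reaching versus maintaining <40.

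A third reply is that Part 2 allocation is balanced on sBA category, so the mix does not bias the between-arm comparison. That is correct for Part 2. It does not make the percentages interpretable, and it does not cover Part 1.

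Finally, the endpoint is exploratory and outside the three-step hierarchy, and sBA lowering is tested as a continuous change adjusted for baseline. This limits the consequence but does not remove the ambiguity.

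**Conclusion.** The point holds as a matter of interpretation and specification, and it is minor. The proportion merges two different outcomes, and the SAP is inconsistent about whether its test is stratified by sBA. Neither conclusion needs an assumed rate.

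A reader might infer that the definition costs power and that the endpoint should be confined to baseline ≥40. The documents do not support that. They give neither the share starting below 40 nor any success rates, and the loss appears only if volixibat does little in that group. On that assumption, at f = 33%, power is about 0.67 unstratified (0.72 with the mix fixed), 0.82 stratified and 0.86 restricted. With 95% versus 75% maintenance the order reverses: 0.92 for all participants against 0.86 restricted.

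Two limits apply. The stratified figures treat the sBA stratum as the same as baseline category, whereas allocation uses the highest earlier value, so more participants may have baseline <40 than the <40 stratum suggests. The 33% share is borrowed from a cap that the current protocol does not contain. The <40 endpoint supports no confirmatory claim.

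**What to change.** Three changes in the SAP, before unblinding:

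1. Keep the all-participant proportion below 40 µmol/L as defined.
2. In SAP 6.2 and 6.3, name the CMH and Mantel-Haenszel strata so that they include the sBA category (<40, 40 to <100, ≥100) in line with the Part 2 allocation factors, and make the list agree with the count of strata. Align the sample code.
3. Report the proportion below 40 separately for baseline ≥40 (achieved) and baseline <40 (maintained), using the baseline value and not the highest earlier one. Do this in both parts, descriptively in Part 1.

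The cost is a few sentences and one extra table, with no new data, visits or participants. The drawback is some sparse strata: 200 participants over 12 cells average about 17 per cell, and some cells will hold far fewer.
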